4.1.3 Planned Assessment Windows

Assessments collected by study week that are collected at early termination visit and unscheduled visits will be assigned to a planned visit window. If the early termination or unscheduled visit day falls into an assessment time window, it will be mapped to the corresponding scheduled analysis visit. Should more than one measurement fall within a visit window, priority is given first to the measurement with a non-missing value in the following order: first, the scheduled assessment; second, an early termination visit; and next, the unscheduled assessment closest to the planned day. In the case that two unscheduled visits are equidistant, the latest will be used. This rule will be applied both to efficacy and safety endpoints. For detailed assessment time window information, please see the above [Table 3](#).

4.1.4 Treatment Start/Stop Dates

Treatment start date will be taken from the “Study Drug Administration-Open Label” eCRF page.

Treatment stop date will be taken from the “Treatment Termination” eCRF page.

Treatment start and stop dates will not be imputed.

4.1.5 Tables and Listings Presentation

Analyses will be performed according to the actual treatment sequence received during the double-blind treatment and open-label extension periods. Treatment sequences ‘Placebo/Difelikefalin’ and ‘Difelikefalin/Difelikefalin’ and all sequences pooled will be displayed in the summary tables and figures. The order of the treatment sequence will be as shown below.

1. Placebo/Difelikefalin
2. Difelikefalin/Difelikefalin
3. Total

The listings will display all the open-label extension period data contained in the eCRF, as well as derived variables.

For continuous variables, rounding in the tables, figures and listings (TFLs) will be defined for each parameter or variable (please refer to [Appendix 2](#)) and the following general rules will be applied:

- The minimum and maximum will be reported with the same number of decimal places as the number of decimals mentioned in [Appendix 2](#).
- The Q1, Q3, mean and median will be reported with 1 more decimal place than the number of decimals mentioned in [Appendix 2](#).
- The SD will be reported with 2 more decimal places than the number of decimals mentioned in [Appendix 2](#).

For categorical variables descriptive statistics, percentages will be presented to 1 decimal place. Percentages will not be presented for zero counts, 100 will be presented with no decimal.

4.1.6 Analysis Populations

Please refer to [Section 3](#) for analysis set.

4.1.7 Pooling of Sites/Country

- Not applicable, this study involves only China as country.

4.1.8 Analysis of Subgroups

- Not applicable.

4.1.9 Methods for Handling and Imputation of Missing Data

Missing data for adverse events (AEs) start and end dates, relationship to study drug, severity, and seriousness, disease diagnosis date or starting dates and laboratory values reported as below the limit of detection or below the limit of quantification or above the upper limit of quantification or above the limit of detection, will be handled as described in this section. No other data will be imputed.

For computation of the time since disease diagnosis (CKD or ESRD) or time on hemodialysis or duration of CKD-associated pruritus, missing dates for disease diagnosis or starting dates will be imputed as follows:

- Completely missing date: no imputation.
- If the month of the date is missing, the month will be imputed to January.
- If the day of the date is missing, the day will be imputed to 1st.
- If the imputed date of first haemodialysis is prior to the imputed or actual CKD date, then set the imputed date of first haemodialysis to the CDK date.

Missing and/or incomplete dates/times for events from “Adverse Event” eCRF page are imputed in a manner resulting in considering them as AEs, which is the worst-case scenario. Stop dates/times will not be imputed if the AE is ongoing.

For identification of AEs, partial, or missing dates for AEs will be imputed as follows:

- Incomplete start date: if the day and month are missing and the year is the same as first administration of study drug of double-blind period, or if only the day is missing, and month and year are the same as first drug administration of double-blind period then the start date is to be replaced by the minimum between first drug administration date of double-blind period and AE resolution date. In all other cases the missing start day or start month is replaced by 01.
- Completely missing start date: the start date is replaced by the minimum between first drug administration date of double-blind period and AE resolution date.
- Incomplete stop dates (month and year available or only year available): these dates are imputed to the last day of the corresponding month, or the last day of the corresponding year if not resulting in a date later than the date of subject's death. In the latter case the date of death will be used to impute the incomplete stop date. In all other cases the incomplete stop date is not imputed.

No other dates will be imputed.

For AE summary tables, a worst-case approach will be followed in the event of missing severity, seriousness, or causality data. If the severity is missing, ‘Severe’ will be imputed. If the seriousness is missing, “Serious”

will be imputed. If causality data is missing, ‘Related to study medication’ will be imputed, exception to this rule will be made for AEs of negative COVID-19 test which will be assumed not to be related to study medication. In the event that no coding information is available for a specific AE, the AE will be presented as an ‘Not Coded’ in summary tables.

In the laboratory analysis dataset and for the computation of the laboratory summary statistics, the values reported as below the limit of detection or below the lower limit of quantification or above the upper limit of quantification or above the limit of detection will be imputed for all visits, excepted for baseline. Laboratory values recorded as $<x$, $\leq x$, $>x$, or $\geq x$ will be displayed in the listings as recorded.

For all calculations,

- laboratory values expressed as ‘less than’ or ‘greater than’ will be imputed using the next numerical value (e.g., ‘ <2.00 ’ will be imputed as 1.99, ‘ >0.3 ’ will be imputed as 0.4).
- laboratory values expressed as ‘less or equal than’ or ‘greater or equal than’ will be imputed using the numerical value (e.g., ‘ ≤ 2.00 ’ will be imputed as 2, ‘ ≥ 0.3 ’ will be imputed as 0.3).

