1 INTRODUCTION

This statistical analysis plan (SAP) describes the statistical methods to be used for the reporting and analyses of the open-label extension period data collected under protocol KOR-CHINA-301 version 2.0 dated 29 March 2022. The statistical analyses for the double-blind period are addressed in a separate SAP.

This SAP should be read in conjunction with the study protocol and case report form (CRF). This version of the SAP has been developed using the protocol dated 29 March 2022 and CRF dated 08 November 2023. Any further changes to the protocol or CRF may necessitate updates to the SAP. Statistical rationale and analysis methods specified in this document take precedence over those described in the protocol, should there be any differences (see [Section 1.2](#) in this document).

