4.8.1 Adverse Events

AEs data are collected from the time the informed consent form (ICF) is signed by the subject. The AE reporting period ends at the last study contact. Missing dates/partial dates of AEs will be handled as per [Section 4.1.9](#).

AEs relative to the open-label extension period are identified as any AE with an onset date on or after the first dose of difelikefalin in the open-label extension period.

All tabular adverse event summaries will only include AEs relative to the open-label extension period.

An AE will be classified as related to study drug if the relationship to study drug was recorded as 'Certain' or 'Probable/Likely' or 'Possible' in eCRF, as determined by the investigator. An AE will be classified as unrelated to study drug if the relationship to study drug was recorded as 'Unlikely' or 'Unrelated' in eCRF as determined by the investigator.

An SAE is defined as an AE when "Is this AE considered as Serious?" on the "Adverse Event" eCRF page is "Yes".

An AE leading to investigational product interruption is defined as an AE where the action taken with study drug is "Drug Interrupted" on the "Adverse Event" eCRF page. An AE leading to investigational product discontinuation is defined as is defined as an AE where the action taken with study drug is "Drug Withdrawn" on the "Adverse Event" eCRF page. An AE leading to early study termination is defined as an AE where other action taken is "Early Study Termination".

Adverse Events of Special Interest (AESI)

An AESI is a medical occurrence specific to the product or program. Any AE with the following MedDRA PT is to be identified as an AESI:

- gait disturbance
- fall
- dizziness
- somnolence
- seizure
- syncope
- mental status changes
- mood altered
- feeling abnormal
- sinus tachycardia, tachycardia, and tachyarrhythmia
- palpitations

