- AEs starting in the double-blind period and leading to study drug discontinuation, early study termination or death in the open-label extension period

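### Missing adverse event start dates are never anchored to the first open-label dose, so true open-label events can drop out of the open-label AE tables

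*SAP*

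**What the plan says.** SAP 4.1.9 has three branches for an incomplete AE start date.

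- No date at all: "Completely missing start date: the start date is replaced by the minimum between first drug administration date of double-blind period and AE resolution date".
- Partial date whose known part matches the first double-blind dose (same year if day and month are missing, same month and year if only the day is missing): the same minimum is used.
- Any other partial date: "In all other cases the missing start day or start month is replaced by 01".

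The section adds that no further dates are imputed. It describes incomplete AE dates as "imputed in a manner resulting in considering them as AEs, which is the worst-case scenario". For the other missing AE attributes it states: "For AE summary tables, a worst-case approach will be followed in the event of missing severity, seriousness, or causality data".

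SAP 4.8.1 defines an open-label AE as "any AE with an onset date on or after the first dose of difelikefalin in the open-label extension period", and then limits the tables: "All tabular adverse event summaries will only include AEs relative to the open-label extension period". It also plans a listing of "AEs starting in the double-blind period and leading to study drug discontinuation, early study termination or death in the open-label extension period" (Listing 16.2.7.3). On the other period, SAP section 1 says: "The statistical analyses for the double-blind period are addressed in a separate SAP".

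**The concern.** The imputation rule and the table definition use different anchors. The rule protects against losing an event as pre-treatment, which is the right question for the double-blind period. In this SAP the question is whether the event began before or after the first open-label dose, and there the rule pushes ambiguous dates to the earlier side. Elsewhere the SAP does anchor to the first open-label dose: general baseline (4.1.2), concomitant medication (4.5.1), and laboratory, ECG and vital sign baselines (4.8.2 to 4.8.4).

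What is at stake is attribution to period. For a placebo/difelikefalin subject, an event on difelikefalin would be given an onset while the subject was on placebo. Under Protocol 12.9.1 it would then belong to the double-blind period. The day-missing losses fall soon after the first open-label dose, which is these subjects' first exposure, and Protocol 2.2 itself argues that reactions to the drug appear early.

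**Working it through.** The plan gives no figure to reproduce, so the check applies the rule to events that truly began in the open-label period.

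**Inputs**
- Double-blind period of 12 weeks, then a gap of up to 1 week (Protocol 4.1 and 8.7.1): the first open-label dose is 12 × 7 = 84 to 84 + 7 = 91 days after the first double-blind dose.
- Open-label treatment of 14 weeks: 14 × 7 = 98 days.
- Mean month 30.4375 days and year 365.25 days (SAP 4.1).
- Assumed: onset uniform over the 98 days, entry uniform over the calendar, resolution on or after onset.

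**Completely missing date.** A true open-label AE resolves after the first double-blind dose, so the minimum is always that dose date, 84 to 91 days too early. Kept: 0%, with no assumption about onset.

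**Day and month missing.** The imputed date is the first double-blind dose (same year) or 1 January. The event is kept only if that 1 January is on or after the first open-label dose. That requires an onset in a later calendar year, or a first open-label dose on 1 January itself.
- Days of onset in a later year, summed over possible dose dates: 97 × 98 / 2 = 4,753. A 1 January dose date adds 98.
- Kept: (4,753 + 98) / 365.25 = 13.3 days on average, and 13.3 / 98 = 13.6%. Lost: about 86%.

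**Day missing.** The onset month is always later than the month of the first double-blind dose, so the date becomes the 1st of the onset month. The event is lost only if its month is that of the first open-label dose and the dose was not on the 1st.
- Mean days lost: (30.4375 − 1) / 2 = 14.7, and 14.7 / 98 = 15.0%. Kept: 85%.
- Mean days of onset in that month: (30.4375 + 1) / 2 = 15.7, about 16% of onsets. Of these only 1 / 15.7 = 6% are kept. In later months 100% are kept.

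**Simulation.** Applying the rule to 400,000 simulated open-label AEs gave the same answers:

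| Start date | Kept in open-label tables |
|---|---|
| Completely missing | 0.000 |
| Day and month missing | 0.136 |
| Day missing, onset over 98 days | 0.850 |
| Day missing, onset in first 28 days | 0.476 |
| Day missing, onset in first 14 days | 0.246 |

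Enumerating every start date in a year gave nearly identical losses for 84-day and 91-day lags.

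**Direction.** Every imputed start is either no later than the first double-blind dose or the first day of the recorded month or year, hence no later than the true onset. No event from before the first open-label dose can be moved to on or after it.

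**Example.** First double-blind dose 13 March 2023, first open-label dose 5 June 2023 (84 days later), true onset 20 June 2023. With the day missing, the start becomes 1 June. With day and month missing, or no date, it becomes 13 March. All three precede 5 June, so the AE is not tabulated.

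**The case against.** The best defence is that the rule does what it set out to do: no event that could have followed the first study dose is lost as pre-treatment, and one anchor gives each AE one onset and one period, consistent with the non-overlapping periods in Protocol 12.9.1. That is true for treatment emergence, but it does not serve the only AE tables this SAP produces.

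Second, few dates may be affected. Subjects are seen at dialysis three times a week, they are asked about health changes since the last visit (Protocol 10.3), and incomplete eCRF data are queried (Protocol 15). A start date with no parts at all is the least likely case. SAEs and AESIs have 24-hour reporting or notification (Protocol 10.7.2 and 10.8.4.2). This stands: the percentages are conditional on a date being incomplete.

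Third, misdated events may still be visible. Listing 16.2.7.3 shows those leading to discontinuation, early termination or death. Listing 16.2.7.1 covers all open-label AEs, and the SAP does not say whether it selects on imputed onset. A listing might therefore show them, but it would not correct the tables. Whether the double-blind tables pick them up depends on the separate SAP, which was not available.

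Fourth, the remedy has its own errors. For day-missing dates with no stop date it is an even trade: 15.0% × 98 = 14.7 days' worth of open-label onsets recovered, against 16.8% × 87.5 (the mean lag) = 14.7 days' worth of double-blind onsets moved in. This also stands, and is why the fix needs a visible count.

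**Conclusion.** The concern holds. For an AE that truly began in the open-label period, an incomplete start date leads to exclusion from the open-label tables in 100% of cases if the date is completely missing, about 86% if only the year is known, and about 15% if only the day is missing. The last figure rises to about 52% or 75% if day-missing onsets fall in the first 28 or 14 open-label days. The 100% is exact; the others rest on uniform onset and uniform calendar entry. Absolute counts cannot be given, because the documents do not state how many dates are incomplete, and they may be small. The point does not threaten the trial's conclusions. It should still be fixed, because a pre-specified rule that can only remove events from a safety table works against the SAP's own worst-case aim.

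**What to change.** Add a clause to SAP 4.1.9 for assigning AEs to the open-label period. The first open-label dose date is imputed as the start if both conditions hold:

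- the known parts of the start date are compatible with that dose (day missing with the same month and year; day and month missing with the same year; or nothing known); and
- the AE did not resolve before that dose.

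Otherwise the present rule stays. Footnote the AE tables with the number of AEs so imputed per treatment sequence, and check against the double-blind SAP for events counted in both periods. Under this clause, 100% of true open-label AEs are kept in all three branches.

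The cost is SAP wording, a few lines of derivation code, and coordination with the double-blind SAP. Some true double-blind AEs, including placebo-period ones, would enter the open-label tables or be counted twice:

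| Start date | Stop date known (assumed duration 0–29 days) | No stop date |
|---|---|---|
| Completely missing | 17% | 100% |
| Day and month missing | 16% | 88% |
| Day missing | 11% | 17% |

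For the open-label tables this is the conservative direction, and the footnote lets a reader see how many events depend on it.

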4.2 Subject Disposition

Subject disposition data will be collected on the “Treatment Termination” and “Study Termination” eCRF pages when a subject completed or discontinued from the treatment and study respectively.

The number of subjects entered the open-label extension period, treated, not treated, completed treatment, or early discontinued treatment from the open-label extension period and from the study during the open-label extension period, along with the discontinuation reasons are to be summarised by treatment sequence and all sequences pooled for the open-label extension period. Additionally, subjects who completed the study will be reported. The following provides the definitions of the aforementioned groups:

- Subjects who entered the open-label extension period are all subjects with a “Yes” noted for the question “Will the subject enter the open-label extension?”.
- Treated subjects are all subjects who received at least one dose of open-label study drug.
- Subjects who completed treatment are all treated subjects with a “No” noted for the question “Did the subject discontinue the treatment prematurely?”.
- Subjects who discontinued treatment are all treated subjects with a “Yes” noted for the question “Did the subject discontinue the treatment prematurely?”.
- Subjects who completed the study are all treated subjects with a “Yes” noted for the question “Did the subject complete the study as per protocol?”.
- Subjects who discontinued the study are all treated subjects with a “No” noted for the question “Did the subject complete the study as per protocol?”.

For all categories, percentages will be calculated using the number of OL-SAF as the denominator.

The number and percentage of subjects having at least one important protocol deviation (PD) during all study periods will be summarized within each category and subcategory of deviations using FAS.

The number and percentage of subjects having at least one not-important PD during all study periods will be summarized within each category and subcategory of deviations using FAS.

The following data will also be presented in the listings:

- Subject disposition data to be presented in a by-subject listing for OL-SAF.
- Inclusion criteria not met/exclusion criteria met data at Day 1 of the open-label extension period to be presented in a by-subject listing for all subjects entered open-label extension period. The subjects are those who with a “Yes” noted for the question “Will the subject enter the open-label extension?” on the “Confirmation to enter open label” eCRF page.
- All the protocol non-compliance data during the open-label extension period will be listed in a by-subject listing for full analysis set.

4.3 Demographics and Baseline Subject Characteristics

Demographic and baseline characteristics were not re-assessed at the start of the open-label extension period, but will be reported for the OL-SAF summarizing data collected prior to the first dose of double-blind period.

Prescription dry body weight is the exception and will be reported both for the double-blind and open-label extension baselines.

Demographic and baseline disease characteristics are to be summarised descriptively by treatment sequence and all sequences pooled for OL-SAF population.

Demographics and baseline characteristics to be summarised include: age (years) at informed consent as a continuous and categorical variable (≥ 18 - < 65 , ≥ 65 - < 85 , ≥ 85 years); gender; race; “If Chinese, both parents are Chinese?” (Yes, No); prescription dry body weight (kg) at double-blind period baseline; prescription dry body weight (kg) at open-label extension period baseline.

All demographic and baseline characteristics data will be provided in by-subject listings.

Baseline disease characteristics variables to be summarised include: baseline weekly mean of the daily 24-hour WI-NRS score, baseline weekly mean of the daily 24-hour WI-NRS score category (moderate (WI-NRS ≥ 4 to < 7) vs. severe (WI-NRS ≥ 7), use/non-use of anti-itch medication during the week prior to randomisation (randomisation stratum), presence/absence of specific medical conditions (randomisation stratum), aetiology of CKD, dialysis type (all reported types and hemodialysis only vs. any other type, dialysis types recorded as other will be reviewed by medical and programmatically categorised as: HD, HDF, HD/HDF, HD/HP, HD/HDF/HP. HDF is the abbreviation for Hemodiafiltration, and HP is the abbreviation for Hemoperfusion), time since first diagnosis of CKD (years), years on hemodialysis, time since the diagnosis of end stage renal disease (ESRD) (years), duration of CKD-associated pruritus (years).

Time (years) since diagnosis date or duration of CKD- associated pruritus as well as time on hemodialysis will be derived as:

$$\frac{\text{date of randomisation} - \text{date of diagnosis or start date of CKD associated pruritus or hemodialysis}}{365.25} + 1$$

For handling of missing or partial dates regarding the diagnosis date or the start date, please refer to [Section 4.1.9](#).

All baseline disease characteristics data will be provided in by-subject listings.

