5.2 Inclusion Criteria

Double-blind Period

The double-blind period of this study will enrol HD subjects with pruritus who meet all the inclusion criteria and none of the exclusion criteria listed below.

1. Subject (or legally accepted representative) has provided written informed consent. Written informed consent must be provided before any study-specific procedures are performed including screening procedures.
2. Chinese subjects aged ≥ 18 to 85 years (inclusive) at the time of consent.
3. Able to communicate clearly with the Investigator and staff, able to understand the study procedures, and able and willing to comply with the study requirements, including providing written responses to questionnaires.
4. Subjects with CKD on HD 3 times weekly for ≥ 12 weeks prior to the informed consent procedure (including the date of informed consent) who can continue HD without changing its frequency or method.

Note 1: Any temporary change in dialysis frequency or method associated with travel or admission to other hospitals with no changes in treatment strategies is acceptable, from the date of informed consent until the end of the follow-up period. Subjects routinely on 4 dialyses a week will not be eligible.

Note 2: Subjects receiving in-home HD may participate as long as they have switched to in-centre HD at least 2 weeks prior to screening and plan to remain on in-centre HD for the duration of the study.

Note 3: Subjects receiving alternate dialysis modalities such as nocturnal dialysis will not be eligible.

5. If female, is not pregnant, or nursing.
6. If female:
 - a. Is surgically sterile; or
 - b. Has been amenorrhoeic for at least 1 year and is over the age of 55 years; or
 - c. Has a negative serum pregnancy test within 7 days before first dose of investigational product and agrees to use acceptable contraceptive measures (e.g., hormonal contraceptives, barrier with spermicide, intrauterine device, vasectomised partner, or abstinence) from the time of informed consent until 7 days after the last dose of investigational product. Note: If the result from serum pregnancy testing at screening is indeterminate due to possible human chorionic gonadotropin elevation secondary to ESRD unrelated to pregnancy, a serum pregnancy re-test may be repeated prior to treatment Day 1 to establish if a negative result can be confirmed.

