4 DESCRIPTION OF THE STATISTICAL ANALYSIS

4.1 General Considerations

The software used for all summary statistics and statistical analyses is SAS® Version 9.4 or later (SAS Institute, Inc. SAS/STAT, Cary, NC, US).

Medical history, AEs, and special situations (if applicable) are to be coded using the MedDRA version 26.0. Prior and concomitant medications are to be coded using the World Health Organization (WHO) Drug Dictionary version Global B3 March 2023. Versions of dictionaries are to be indicated in the footnote of the relevant tables and listings.

For the purpose of conversion of year/month to days, the following convention will be used:

- 1 year = 365.25 days
- 1 month = 30.4375 days

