4.6 Study Drug Exposure and Compliance

Study drug exposure and compliance are to be summarized and listed for OL-SAF population.

Study drug exposure data during open-label extension period will be collected on the “Study Drug Administration-Open label” eCRF page and the dialysis data will be collected on the “Dialysis-Open label” and “Dialysis Type Adjustment” eCRF page. Note that dialyses after last dose may be collected on the “Dialysis-Open Label” eCRF page. Only dialysis from open-label extension period Day 1 until the last dialysis prior to EoT or ET visit will be included as dialysis during the open-label extension period.

For this study, the duration of open-label treatment for each individual subject is expected to be 14 weeks, for a total of approximately 42 doses of study drug administered immediately following each dialysis session. The last day of the open-label treatment period will be defined as the day of the last injection of investigational product + 2.5 days, as there would be 2-3 days from the last dose to the next dialysis.

Study drug administration and treatment compliance during the open-label extension period is to be summarised by treatment sequence and all sequences pooled by the following parameters:

- Duration of open-label treatment (days): calculated as (date of the last dose + 2.5) – (date of first dose) + 1
- Total number of doses actually received as continuous and categorical variables (1-3, 4-6, 7-9, etc.)
- Number of missed doses as continuous and categorical variables (1-3, 4-6, 7-9, etc.)
- Average dose per administration (mcg/kg): calculated as actual dose (ml) * 50 mcg/ml (strength) / prescription dry body weight (kg). Noted the prescription dry body weight is to be captured on Day1 and at Week 12 during the open-label extension period. The most recent value is to be used for the calculation.
- Average dose per administration (mcg): calculated as actual dose (ml) * 50 mcg/ml (strength)
- Number of subjects with extra doses: (1, 2, 3, >=4 doses)
- Compliance (%): calculated as actual doses/planned doses (defined below)

Dialysis performed during the open-label extension period is to be summarized by treatment sequence and all sequences pooled by the following parameters:

- Total number of dialysis visits logged as a continuous and categorical variable (1-3, 4-6, 7-9, etc.)
- Number of missed dialysis visits as a continuous and categorical variable (1-3, 4-6, 7-9, etc.)

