Appendix 2: Unit and Decimal Place

Parameters/Variables	Unit	Number of decimals
Age	years	0
Dry body weight	kg	1
Time since first diagnosis of CKD	years	1
Years on hemodialysis	years	1
Time since diagnosis of ESRD	years	1
Duration of CKD-associated pruritus	years	1
Duration of open-label treatment	days	0
Total number of doses actually received	times	0
Number of missed doses	times	0
Average dose per administration	mcg/kg	1
Average dose per administration	mcg	0
Number of extra doses	times	0
Total number of dialysis visits logged	times	0
Number of missed dialysis visits	times	0
Number of extra dialysis visits	times	0
Compliance	%	1
Albumin	g/L	1
AST/SGOT, Aspartate Aminotransferase	U/L	0
ALT/SGPT, Alanine Aminotransferase	U/L	0
Alkaline Phosphatase	U/L	0
Bilirubin (Total)	µmol/L	2
Glucose	mmol/L	2
Creatinine	µmol/L	0
Bun, Blood Urea Nitrogen	mmol/L	2
Sodium	mmol/L	0
Potassium	mmol/L	2
Chloride	mmol/L	1
Calcium	mmol/L	2
Phosphorus	mmol/L	2
Haemoglobin	g/L	0
Haematocrit	%	1
Platelet	×10 ⁹ /L	0
White Blood Cells	×10 ⁹ /L	2
Neutrophil (Absolute)	×10 ⁹ /L	2
Neutrophil %	%	1
Eosinophil (Absolute)	×10 ⁹ /L	2
Eosinophil %	%	1
Basophil (Absolute)	×10 ⁹ /L	3
Basophil %	%	1
Lymphocyte (Absolute)	×10 ⁹ /L	2
Lymphocyte %	%	1
Monocyte (Absolute)	×10 ⁹ /L	2
Monocyte %	%	1
Red Blood Cells	×10 ¹² /L	2
MCV, Mean Corpuscular Volume	fL	1
MCH, Mean Corpuscular Haemoglobin	pg	1
MCHC, Mean Corpuscular Haemoglobin Concentration	g/L	0
RDW, Red Blood Cell Distribution Width	%	1
β-HCG from Serum Pregnancy Test	IU/L	3
Body temperature	C	1

Parameters/Variables	Unit	Number of decimals
Respiratory rate	breaths/min	0
Radial pulse rate	beats/min	0
Systolic blood pressure	mmHg	0
Diastolic blood pressure	mmHg	0
Heart rate	Beats/Min	0
QT Interval	msec	0
QTcF Interval	msec	0
QTcB Interval	msec	0
RR Interval	sec	1
P-wave	msec	0
QRS complex duration	msec	0
PR Interval	msec	0

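### As printed, the SAP 4.3 formula for disease durations adds 1 after dividing by 365.25, so each derived value is about one year too long; only descriptive baseline output is affected.

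*SAP*

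**What the plan says.** SAP 4.3 lists four durations in years among the baseline disease characteristics: time since first CKD diagnosis, years on haemodialysis, time since ESRD diagnosis, and duration of CKD-associated pruritus. One displayed formula covers them, introduced by "Time (years) since diagnosis date or duration of CKD- associated pruritus as well as time on hemodialysis will be derived as". Its numerator is the date of randomisation minus the "date of diagnosis or start date of CKD associated pruritus or hemodialysis". Its denominator is 365.25. A +1 follows the fraction.

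Four other places bear on it:

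- SAP 4.1 fixes the conversion: "1 year = 365.25 days".
- SAP 4.6 gives the duration of open-label treatment in days, "calculated as (date of the last dose + 2.5) – (date of first dose) + 1". The +1 there is added to a number of days.
- SAP Appendix 2 sets the reporting precision, for example "Duration of CKD-associated pruritus years 1", meaning years to one decimal. SAP 4.1.5 gives means, medians and quartiles one more decimal.
- Protocol 12.5 names duration of pruritus and years on HD as baseline characteristics but gives no formula.

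SAP section 1 says that its methods take precedence over the protocol's, so the SAP 4.3 formula is the operative definition for these outputs.

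**The concern.** A +1 in a duration formula is normally an inclusive-day correction: it counts both end dates, and it belongs with the days. Placed after the division by 365.25, it adds a year.

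The printed rule also gives values that cannot be right. A subject whose start date is the day of randomisation would score 1.0 year, and nobody with a start date on or before randomisation could score less. Yet Protocol 5.2 admits "Subjects with CKD on HD 3 times weekly for ≥ 12 weeks prior to the informed consent procedure", so a subject with well under a year on haemodialysis can enter.

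At stake is the accuracy of four descriptive variables in the baseline table and its listing. If programmed literally, the table would describe a population with kidney disease, dialysis and itch of about a year longer standing than it has.

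**Working it through.** The documents give no worked value for these variables, so there is no figure to reproduce. The check is direct arithmetic.

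**Inputs.** d is the number of days from the diagnosis or start date to randomisation (SAP 4.3). One year is 365.25 days (SAP 4.1). The shortest qualifying time on three-times-weekly HD is 12 weeks = 84 days, counted to consent (Protocol 5.2). Randomisation comes after consent, so 84 days is a convenient lower bound.

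**Formulas.**

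- As printed: P = d/365.25 + 1
- Inclusive days: A = (d + 1)/365.25
- Plain difference: B = d/365.25

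**Error.**

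- P − A = 1 − 1/365.25 = 0.9973 year
- P − B = 1 year
- A − B = 1/365.25 = 0.0027 year

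None of these depends on d, so the shift is the same for every subject with a derived value.

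| d (days) | P, as printed | A, inclusive | B, plain | P/A |
|---|---|---|---|---|
| 0 | 1.000 | 0.003 | 0.000 | – |
| 84 | 1.230 | 0.233 | 0.230 | 5.29 |
| 365 | 1.999 | 1.002 | 0.999 | 2.0 |
| 730 | 2.999 | 2.001 | 1.999 | 1.5 |
| 1826 | 5.999 | 5.002 | 4.999 | 1.2 |
| 3652 | 10.999 | 10.001 | 9.999 | 1.1 |

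The relative overstatement is large for short durations and falls to about 20% at five years and 10% at ten.

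**Effect on the summaries.** A constant shift moves the mean, median, quartiles, minimum and maximum by the same 0.997 to 1.000 year. It leaves the SD and any difference between treatment sequences unchanged. At one or two decimals of a year, a shift of about 1.0 shows in full.

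**Effect on the analyses.** The MMRM in SAP 4.7 contains treatment sequence, week, their interaction, baseline score and the stratification variables. The logistic models contain treatment sequence, baseline score, anti-itch medication use and specific medical conditions. None of the four durations appears. SAP 4.1.8 plans no subgroup analysis, and SAP 4.8 makes the safety analyses descriptive by sequence. None of these results changes.

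**The case against.** The strongest reply is that the point rests on the position of one symbol relative to a fraction bar, in a formula read from PDF by a program. No sentence or worked example elsewhere confirms it. That is a good reason to look at the source page and the code before acting. It does not answer the point, because the text available places the +1 outside the fraction and nothing else in the SAP corrects it.

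A second reply is that the intended formula is unknown. The SAP does not say that the +1 was meant as an inclusive-day correction here, and a plain difference over 365.25 fits SAP 4.1 equally well. This stands, but it matters little, since the two candidates differ by less than 0.003 year.

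A third reply is that the effect is small. This stands too: the four variables are descriptive and enter no model.

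Four stronger readings are tempting, and the documents do not support them:

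- A reader might infer that the error spoils comparison with the earlier difelikefalin trials. Neither document gives these durations that use; they are only summarised and listed.
- A reader might take SAP 4.6 as a second instance. It is not: the +1 there is added to days.
- A reader might assume that the baseline table of the whole randomised population is wrong as well. This SAP covers only the open-label extension. The double-blind period has a separate SAP that was not available for review.
- A reader might say that every subject's record is wrong. SAP 4.1.9 does not impute completely missing dates, so those subjects have no value to overstate.

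**Conclusion.** The formula is wrong as written. Each derived value of the four durations is too long by 0.997 year against an inclusive-day count, or by 1 year against a plain difference. The conclusion assumes that the +1 stands on the source page where the extracted text puts it; whether reported values are affected also depends on the code following the printed formula.

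The consequence is confined to the baseline disease characteristics of the open-label safety set, in Table 14.1.3.2 and Listing 16.2.4.2. Location statistics shift by about 1.0 year; spread and between-sequence differences do not. Efficacy and safety results, power and type I error are untouched. It is worth correcting because reported values would be false, not because any inference is at risk.

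**What to change.** 1. Check the position of the +1 on the source page of SAP 4.3 and in the derivation code for the four variables.
2. If it is outside the fraction, write the formula as (date of randomisation − start date + 1)/365.25, or omit the +1. Either is acceptable; the sponsor should choose one and state it.
3. If the code followed the printed formula, rerun Table 14.1.3.2 and Listing 16.2.4.2.
4. Check whether the double-blind SAP and its baseline table use the same formula, because these are data from before the first double-blind dose and the two reports should agree.

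SAP 4.6 needs no change on this account. The cost is one line in the SAP and, if the code is affected, one derivation and two outputs. No new data are needed.
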